### 5.2 Exclusion Criteria

An individual who meets any of the following criteria will be excluded from participation in this study:

1. Age < 18 years.

### 5.3 Vulnerable Subjects

Vulnerable populations will not be included.

### 5.4 Strategies for Recruitment and Retention

Patients will be recruited from investigator clinical practices. The recruitment plan does not propose to use any NYULMC media services or social media. Patients with clinically diagnosed wrist pathology undergoing wrist arthroscopy will be identified by the attending physician and recruited for the study in the office visit when surgery is indicated/scheduled or in the pre-operative area on the day of surgery. The nature of the information the subjects will be asked to give about themselves will include objective information relevant to their wrist injury. Only the individuals listed in the protocol will have access to the patients study.

As this study does not require long-term patient participation, there are no relevant modalities necessary to enhance participant retention.

The target sample size is 34 patients, recruited from the investigators clinical practice.

Study number: i20-00356 Page 14 Version: June 8, 2020

### 5.4.1 Use of DataCore/Epic Information for Recruitment Purposes

We will not be using DataCore/Epic for recruitment purposes.

### 5.5 Duration of Study Participation

The duration of the study participants' participation will be one day.

### 5.6 Total Number of Participants and Sites

Recruitment will end when approximately 34 participants are enrolled. It is expected that approximately 34 participants will be enrolled in order to produce 34 evaluable participants. Participants will be enrolled at four 4 NYU study sites:

- 1. NYU Langone Orthopedic Hospital
- 2. Tisch Hospital, NYU Langone Health
- 3. NYU Langone Orthopedic Center (38th Street)
- 4. Joan H. & Preston Robert Tisch Center at Essex Crossing, NYU Langone Health

### 5.7 Participant Withdrawal or Termination

### 5.7.1 Reasons for Withdrawal or Termination

Participants are free to withdraw from participation in the study at any time upon request. An investigator may terminate participation in the study if:

- Any clinical adverse event (AE), laboratory abnormality, or other medical condition or situation occurs such that participation in the study
  would not be in the best interest of the participant.
- The participant meets an exclusion criterion (either newly developed or not previously recognized) that precludes study participation.

### 5.7.2 Handling of Participant Withdrawals or Termination

Participants who withdraw from the study will continue routine post-operative follow up with the PI for wrist injury. Their continued care will not be affected by their enrollment in this study.

### 5.8 Premature Termination or Suspension of Study

Not applicable.

Study may resume once concerns about safety, protocol compliance, data quality are addressed and satisfy the sponsor, IRB and/or FDA.

# 6 Study Agent (Study drug, device, biologic, vaccine etc.) and/or Procedural Intervention

The procedural intervention will be a diagnostic wrist arthroscopy using the Arthrex NanoScope followed by a diagnostic wrist arthroscopy using conventional wrist arthroscopy equipment.

### **6.1.1 Device Specific Considerations**

Instrument: Arthrex NanoScope - Nano Operative Arthroscopy System

Study number: i20-00356 Page 15 Version: June 8, 2020

- 1.9 mm single-use, needle-size sterile camera.
- 13" medical grade 3-in-1 camera control unit.
- This device is currently in use for wrist arthroscopy. The intended purpose of this research study is to compare this devices diagnostic accuracy to conventional larger arthroscopic equipment.
- https://www.arthrex.com/hand-wrist/nano-arthroscopy-system-for-hand-and-wrist

### 6.2 Study Behavioral or Social Intervention(s)

### 6.2.1 Administration of Intervention

The attending physician will perform the diagnostic arthroscopy.

### 6.2.2 Procedures for Training Interventionalists and Monitoring Intervention Fidelity

The use of conventional arthroscopic instruments and the Arthrex NanoScope are considered standard of care, and clinicians do not require additional training for either.

### 6.2.3 Assessment of Subject Compliance with Study Intervention

Not applicable.

### 6.3 Study Procedural Intervention(s) Description

Diagnostic arthroscopy is a well-established procedure. The procedure itself is not considered the study intervention. Use of the NanoScope using standard extremity stabilization tower and standard wrist arthroscopy portals will be employed. The instrumentation is similar to conventional arthroscopic instrumentation with exception of size, therefore additional training is not required for its use.

https://www.arthrex.com/hand-wrist/nano-arthroscopy-system-for-hand-and-wrist

### 6.3.1 Administration of Procedural Intervention

The attending physician will perform the diagnostic arthroscopy.

### 6.3.2 Procedures for Training of Clinicians on Procedural Intervention

The intervention will be standardized by having a single operator (attending) perform the diagnostic arthroscopy with the Arthrex NanoScope and conventional instruments. The diagnostic arthroscopy will be performed in a stepwise manner evaluating the ligaments and articular surfaces of the wrist.

# 6.3.3 Assessment of Clinician and/or Participant Compliance with Study Procedural Intervention

Physician compliance with procedural intervention will be through review of the medical record/operative report.

Version: June 8, 2020 **7 Study Procedures and Schedule** 

# 7.1 Study Procedures/Evaluations

### 7.1.1 Study Specific Procedures

- Patients undergoing wrist arthroscopy for diagnostic evaluation and treatment of a wrist injury will be enrolled pre-operatively following a
  discussion of the study, risks, benefits, and informed consent.
- All patients will be positioned supine and placed in an upper extremity traction tower with the shoulder abducted, elbow flexed to 90 degrees, forearm in neutral position.
- Standard arthroscopic portals will be made for viewing, instrumentation, inflow, and outflow: 3-4 portal, 6-R portal, midcarpal ulnar (MCU) portal, +/- midcarpal radial (MCR) portal, +/- 6-U portal.
- A diagnostic arthroscopy will be performed with the Arthrex NanoScope.
  - Structures evaluated:
    - Radial styloid
    - Proximal scaphoid articular cartilage
    - Scaphoid fossa
    - Radioscaphocapitate (RSC) ligament
    - Long radiolunate (LRL) ligament
    - Short radiolunate (SRL) ligament
    - Scapholunate (SL) ligament
    - Proximal lunate articular cartilage
    - Lunate fossa
    - Triangular fibrocartilage complex (TFCC)
  - The attending performing the diagnostic arthroscopy will make an initial diagnostic assessment based on the presence/location/severity of synovitis, articular cartilage integrity, ligament injury and determine the intended treatment.
- A diagnostic arthroscopy will then be performed with the standard arthroscopic instruments.
  - Structures evaluated:
    - Radial styloid
    - Proximal scaphoid articular cartilage
    - Scaphoid fossa
    - Radioscaphocapitate (RSC) ligament
    - Long radiolunate (LRL) ligament
    - Short radiolunate (SRL) ligament
    - Scapholunate (SL) ligament
    - Proximal lunate articular cartilage
    - Lunate fossa
    - Triangular fibrocartilage complex (TFCC)
  - The attending performing the diagnostic arthroscopy will make the final diagnostic assessment based on the presence/location/severity of synovitis, articular cartilage integrity, and ligament injury and determine the final treatment.

Study number: i20-00356 Page 17 Version: June 8, 2020

- Following the procedure the surgeon will perform a short questionnaire.
  - Surgeon rated visualization. (5 point scale)
  - Surgeon-rated ease of use. (5 point scale)
  - o Surgeon-rated diagnostic confidence. (5 point scale)
- The initial diagnostic assessment and final diagnostic assessment will be compared to determine diagnostic accuracy of the Arthrex NanoScope.
- "Intended" treatment and "final" treatment will be compared to determine if diagnostic variability would result in potential treatment variability.
- Patients with pre-operative MRIs with a corresponding radiology report will be compared to arthroscopic findings to determination correlation between MRI and arthroscopy.
- No follow-up is required for the purposes of this study.

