# **Schematic of Study Design**

N = 34: Obtain informed consent from patients scheduled to undergo wrist arthroscopy at NYU Langone Health. Screen for inclusion and exclusion criteria; obtain history, document.

Perform diagnostic wrist arthroscopy with standard portals using NanoScope.

Perform NanoScope Assessment:

- 1. Diagnosis.
- 2. Intervention (intended).
- 3. Ease of use.
- 4. Diagnostic confidence.

Perform diagnostic wrist arthroscopy with standard portals using conventional instruments.

Perform Conventional Assessment:

- 1. Diagnosis.
- 2. Intervention.
- 3. Ease of use.
- 4. Diagnostic confidence.

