### 3.2 Secondary Objectives (if applicable)

To determine if the diagnostic accuracy of the Arthrex NanoScope compared to conventional arthroscopic instruments results in a change in intended intervention.

To determine the surgeon-rated ease of use and diagnostic confidence of the Arthrex NanoScope.

To determine the diagnostic correlation between pre-operative MRI and arthroscopy (NanoScope and conventional). The MRI is standard of care for evaluation of ligamentous wrist pathology. It will not be mandated as part of the protocol.

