### 10.3.3 Analysis of the Secondary Endpoint(s)

### Secondary

- 1. Incidence of change in intervention.
- 2. Surgeon rated ease of use.
- 3. Surgeon rated confidence of diagnosis.
- 4. Correlation between pre-operative MRI findings and arthroscopic findings.

Secondary endpoints will be described using incidence/percentage. A two-tailed Student's T-tests will be employed to compare the means of surgeon-rated outcomes between the Arthrex NanoScrope and conventional instruments groups with a p value of .05.

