### 10.5.2 Evaluation of Success of Blinding

Blinding is not possible and not indicated for this study design.

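### The schematic has the NanoScope's ease of use and diagnostic confidence rated before the conventional look; section 7.1.1 puts the rating after both looks, when the reference finding is known

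*Combined protocol and SAP*

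**What the plan says.** The Schematic of Study Design gives four steps in order. The NanoScope look comes first. Next is "Perform NanoScope Assessment", whose items are diagnosis, intended intervention, ease of use and diagnostic confidence. Then comes "Perform diagnostic wrist arthroscopy with standard portals using conventional instruments". Last is "Perform Conventional Assessment", which again includes ease of use and confidence.

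Section 7.1.1 describes the same day differently. Between the two looks the attending records only an initial diagnosis and an intended treatment. After the second look come the final diagnosis and final treatment. Only then does it say: "Following the procedure the surgeon will perform a short questionnaire". The form has three 5-point items (visualization, ease of use, diagnostic confidence) and the section does not say which scope they describe.

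The Brief Summary in the Protocol Summary says that ease of use and confidence will be determined post-operatively, in the same sentence as diagnostic accuracy and change in intervention.

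Section 3.2 states the objective for one instrument: "To determine the surgeon-rated ease of use and diagnostic confidence of the Arthrex NanoScope". Section 10.3.3 plans a t-test to "compare the means of surgeon-rated outcomes between the Arthrex NanoScrope and conventional instruments groups". Section 6.3.2 standardizes the procedure by "having a single operator (attending) perform the diagnostic arthroscopy with the Arthrex NanoScope and conventional instruments", and section 10.5.2 states: "Blinding is not possible and not indicated for this study design".

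**The concern.** Conventional arthroscopy is the study's gold standard, and the same surgeon performs both looks. A surgeon who rates confidence in the NanoScope diagnosis after the conventional look knows whether that diagnosis was confirmed. The rating then partly measures whether the call proved right, not how sure the surgeon was when making it. Ease of use and visualization may also be coloured by having just used the second scope.

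Two analyses use these ratings. One is the between-instrument comparison in 10.3.3. The other is the exploratory relation of accuracy to ease of use and confidence in 4.2.3. In the second, a confidence score given after agreement is known is partly determined by the accuracy it is being related to. Section 4.2.1 gives the study's aim as showing whether the smaller scope could serve as the only means of evaluation; confidence before any second look is the rating that fits that use. It cannot be recovered once the case is over.

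**Working it through.** **Step 1: order of events, side by side.**

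| Point in the procedure | Schematic | Section 7.1.1 |
|---|---|---|
| After NanoScope look | Diagnosis, intended intervention, ease of use, confidence | Initial diagnosis, intended treatment |
| After conventional look | Diagnosis, intervention, ease of use, confidence | Final diagnosis, final treatment |
| After that | None | One questionnaire: visualization, ease of use, confidence; instrument not named |

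Both place the NanoScope diagnosis and intended treatment before the second look. They differ on when the NanoScope ratings are made.

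**Step 2: do other sections settle it?** *Which instrument:* largely yes. The schematic lists ratings under both assessments, and 10.3.3 compares means between the two, which needs a rating of each. Section 3.2 is narrower but does not say that the conventional scope goes unrated. *When:* no. The Protocol Summary may mean that the ratings are made post-operatively, which supports 7.1.1, or only that results are worked out then, since accuracy is in the same list.

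**Step 3: can a size be given?** The plan states no figure to reproduce. It gives n = 34 and a 5-point scale, but no rating SD, no correlation between the two ratings, no shift, and no expected disagreement between scopes. It is tempting to take disagreement from 10.4 as 31 × (1 − 0.90) = 3.1 wrists. But the 0.90 there is the sensitivity of arthroscopy, set against 0.70 for MRI; it is not NanoScope-versus-conventional agreement. What follows is therefore illustrative only.

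Assumptions: n = 34; latent ratings normal with mean 4 and SD 0.8; shift added, then rounded and clipped to 1–5; no true difference between scopes; two-sided 0.05; 40,000 simulated trials per cell; 3 or 6 discordant wrists. The expected mean shift before rounding and clipping is

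(number discordant × mark-down + number concordant × mark-up) / 34.

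- 3 discordant at −0.5, no mark-up: (3 × −0.5)/34 = −0.044
- 3 discordant at −1, no mark-up: −3/34 = −0.088
- 6 discordant at −1, no mark-up: −6/34 = −0.176
- 3 discordant at −0.5, the other 31 marked up 0.25: (−1.5 + 7.75)/34 = +0.184

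Simulated mean shift and false-difference rate (nominal 5%; unpaired/paired t-test, since the plan does not say which):

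| Scenario | Mean shift | Ratings uncorrelated | Correlation 0.5 |
|---|---|---|---|
| No shift | 0 | about 5/5% | about 1/5% |
| 3 at −0.5 | −0.04 | about 5/5% | about 1/6% |
| 3 at −1 | about −0.085 | about 6/6% | about 2/7% |
| 6 at −1 | −0.17 | about 12/12% | about 6/16% |
| 3 at −0.5, 31 at +0.25 | +0.16 | about 13/13% | about 7/18% |

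The second and last rows differ only in whether confirmed calls are marked up, and the sign reverses. On the unrounded scale a mark-up of 1.5/31 = 0.048 point on the concordant calls is enough to cancel the mark-down in the second row. Knowing the outcome could plausibly move ratings both ways, so the direction is a modelling choice and not a result.

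**The case against.** The strongest reply is that this is one loosely worded bullet. The form itself is not in the documents. It may have a column for each scope, and the words about following the procedure could mean after each look, which would agree with the schematic. Much of this is fair. The columns point stands, and it is why the question of which instrument is rated is not the main issue here. But two columns completed at the end do not restore the timing. The singular questionnaire, listed after the final treatment decision, makes the after-both reading the more natural one. If rating after each look was intended, one sentence would say so.

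It is also fair that little hangs on it: the ratings are secondary and subjective, and section 10.3.8 plans no exploratory analysis, so the relation in 4.2.3 has no test. That bears on priority, not on whether the sections conflict.

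Three stronger readings are tempting, and the documents do not support them:

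- A reader might infer that the accuracy result is contaminated. It is not contaminated by this route, because both descriptions record the NanoScope diagnosis and intended treatment before the second look.
- A reader might infer that the conventional scope is never rated. The schematic and 10.3.3 show otherwise.
- A reader might infer that NanoScope confidence will be understated, or that the effect is known to be small. Step 3 shows that both conclusions depend on assumed shifts.

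**Conclusion.** The point holds as a conflict over timing. The schematic has the NanoScope rated before the reference look, section 7.1.1 has one unlabelled form after both looks, and the Protocol Summary leans towards the later timing without settling it. That the sections differ is certain. That bias would follow is conditional: it requires that 7.1.1 is followed as written and that knowing the outcome influences the surgeon's score.

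If so, the secondary comparison in 10.3.3 and the relation in 4.2.3 could be biased in either direction, by an amount the documents do not allow to be derived. The simulated false-difference rates, from about 1% to 18% across the assumed scenarios and both forms of the t-test, show only how far the answer depends on the inputs; they are not an estimate for this trial. The primary endpoint is not affected. The change should be made because the bias is avoidable at little cost and the protocol's own schematic already avoids it, not because the effect is shown to be large.

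**What to change.** Bring section 7.1.1 and the Protocol Summary into line with the schematic's order:

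- Record NanoScope visualization, ease of use and confidence together with the initial diagnosis and intended treatment, before the conventional scope is introduced.
- Record the same three items for the conventional scope after the second look. Visualization appears in 7.1.1 but not in the schematic, so add it there.
- Name the instrument on each form.
- Make section 3.2 agree with 10.3.3 that both instruments are rated.
- If a direct side-by-side judgement is wanted, keep it as a separately labelled item after both looks.

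The cost is a form change, a few reconciling sentences, and a brief pause for three 5-point ratings. The pause falls within the operation, so it should be counted with the under-5-minute extra time estimated in section 2.4.1. No extra patients, assessors or procedures are needed.

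The change removes hindsight from the NanoScope ratings only. The NanoScope always comes first, so contrast and order effects in the conventional rating remain, as does any comparison made by a surgeon already familiar with both scopes. The 10.3.3 comparison should be reported with that limitation.

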# **Protocol Summary**

Title	A Comparative Study Evaluating the Diagnostic Accuracy of Wrist Arthroscopy Using the NanoScope Compared to Conventional Arthroscopic Instrumentation
Short Title	Wrist Arthroscopy Study
Brief Summary	The purpose of this study is to evaluate the diagnostic efficacy of Arthrex NanoScope compared to conventional arthroscopic instruments. Patients with wrist pathology who are indicated for an arthroscopic procedure will be enrolled pre-operatively after a thorough discussion of the study aims, risks, and benefits. At the time of surgery, under standard conditions, using standard wrist arthroscopy portals, a diagnostic arthroscopy will be performed with the Arthrex Nanoscope. The diagnostic arthroscopy will be performed in a stepwise manner for consistency with notation of pathology and intended intervention. The diagnostic arthroscopy will then be performed with the standard arthroscopic equipment, again noting pathology and final intervention. Post-operatively, diagnostic accuracy, incidence of change in intervention, and surgeon rated ease of use and confidence will be determined.
Phase	Not applicable
Objectives	Primary Outcome: To compare the diagnostic sensitivity and specificity of the NanoScope compared to conventional arthroscopic instruments.  Secondary Outcome: To determine if the diagnostic variability between NanoScope and conventional arthroscopic instruments results in a change in intervention. Surgeon-rated ease of use. Surgeon-rated diagnostic confidence.  Secondary Outcome: To determine the diagnostic correlation between preoperative MRI and arthroscopy (NanoScope and conventional).
Methodology	Prospective Cohort Study, Diagnostic

Study number: i20-00356 Version: June 8, 2020

[figure not shown]
Primary	Primary  1. Diagnostic accuracy of Nanoscope compared to conventional arthroscope.  Secondary  1. Incidence of change in intervention.  2. Surgeon rated ease of use.  3. Surgeon rated confidence of diagnosis.
21.1.2.11	4. Comparative correlation between pre-operative MRI and arthroscopy.
Study Duration	1 year
Participant Duration	1 day
Duration of IP administration	Not applicable
Population	N = 34, men and women, age ≥ 18 years, being treated at NYU Langone Health
Study Sites	
 
NYU Langone Orthopedic Hospital
 
Tisch Hospital, NYU Langone Health
 
NYU Langone Orthopedic Center (38th Street)
 
Joan H. & Preston Robert Tisch Center at Essex Crossing, NYU Langone Health
 

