### 4.2.2 Secondary Study Endpoints

Version: June 8, 2020

Secondary endpoints will be a incidence of change in intended intervention and surgeon-rated ease of use and diagnostic confidence.

These secondary endpoints were chosen to determine if a difference in diagnostic accuracy results in a change in intervention as well as to determine the number of uses required for surgeon familiarity with the instruments.

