### 7.5 Prohibited Medications, Treatments, and Procedures

Treatment with additional upper extremity surgical procedures will not be permitted unless discussed with and approved by the principal investigator.

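### The planned change-in-intervention rate is never related to whether the two scopes gave different diagnoses, which is what the secondary objective asks

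*Combined protocol and SAP*

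**What the plan says.** The objective is worded as a link in three places. The Protocol Summary has "To determine if the diagnostic variability between NanoScope and conventional arthroscopic instruments results in a change in intervention". Section 3.2 asks whether NanoScope accuracy relative to the conventional scope "results in a change in intended intervention". Section 4.2.2 gives the reason for the endpoint as to "determine if a difference in diagnostic accuracy results in a change in intervention".

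Section 7.1.1 sets out the data. After the NanoScope look the attending makes an initial diagnostic assessment and determines an intended treatment. After the conventional look the same attending makes a final assessment and determines a final treatment. Ten structures are listed for each look. The comparison is then described: "Intended' treatment and 'final' treatment will be compared to determine if diagnostic variability would result in potential treatment variability".

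The analysis is in section 10.3.3: "Secondary endpoints will be described using incidence/percentage". The t-test named there is for the surgeon ratings. Section 10.3.8 lists exploratory analyses as not applicable. Section 10.1 defers a formal SAP to before database lock.

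**The concern.** The objective has two parts, a diagnostic difference and a treatment change, and asks whether the first leads to the second. The planned result uses only the second. A treatment plan can change between two consecutive looks without any difference in recorded diagnosis, for example because the surgeon reconsiders on seeing the joint again. An overall percentage pools such changes with those that accompany a diagnostic difference.

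Section 4.2.1 says the study is meant to inform whether the smaller scope can be the only means of evaluation. For that use, the change rate is the measure of what a NanoScope misreading would have done to the treatment plan. If it cannot be related to disagreement, a high rate may be read as a consequence of NanoScope error when it is partly something else. A low rate may be read as reassurance when it reflects only that few wrists were discordant.

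**Working it through.** **Is the link analysed anywhere?**
- Section 10.3.3 gives a percentage only.
- Section 10.3.1 offers a chi-squared test for categorical variables, but between the two treatment groups (the scopes), not between change and disagreement within wrists.
- The exploratory endpoint in 4.2.3 concerns accuracy against ease of use and confidence, and 10.3.8 plans no exploratory analysis.
- Section 10.3.7 lists individual data by measure. A listing makes the link recoverable but is not an analysis of it.

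**Plan's own figure.** There is none for this endpoint. The 34 participants in 10.4 come from a sensitivity comparison (0.70 against 0.90), so there is nothing to reproduce here.

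**What a crude rate can hide.** The following are assumptions, not taken from the documents. Let d be the proportion of wrists with discordant diagnoses, c = 0.5 the chance that a discordance changes the plan, and b the chance of a change for any other reason, independent of diagnosis.

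- Crude rate = 1 − (1 − d·c)(1 − b).
- Share of the crude rate not due to diagnosis = (crude − d·c) / crude.

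At d = 10%:
- b = 0: crude 5.0%, share 0%.
- b = 5%: 1 − 0.95 × 0.95 = 9.75%, share (9.75 − 5.0)/9.75 = 49%.
- b = 10%: 1 − 0.95 × 0.90 = 14.5%, share (14.5 − 5.0)/14.5 = 66%.

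At d = 20%, b = 5%: 1 − 0.90 × 0.95 = 14.5%, share (14.5 − 10.0)/14.5 = 31%.

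Over d from 5% to 20% and b from 3% to 10%, the share runs from 21% to 80%.

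The last two cases listed give the same crude rate with different answers to the objective. In 34 wrists, 14.5% is 4.93, or about 5. Expected counts are:
- Case A (d = 10%, b = 10%): 3.4 discordant wrists with 3.4 × 0.55 = 1.87 changes; 30.6 concordant with 30.6 × 0.10 = 3.06.
- Case B (d = 20%, b = 5%): 6.8 discordant wrists with 6.8 × 0.525 = 3.57 changes; 27.2 concordant with 27.2 × 0.05 = 1.36.

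Here 0.55 = 1 − 0.5 × 0.90 and 0.525 = 1 − 0.5 × 0.95. Rounded to whole wrists, with exact (Clopper-Pearson) 95% intervals:

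| | Overall | Discordant wrists | Concordant wrists |
|---|---|---|---|
| Case A | 5/34 = 14.7% (5.0 to 31.1) | 2/3 = 66.7% (9.4 to 99.2) | 3/31 = 9.7% (2.0 to 25.8) |
| Case B | 5/34 = 14.7% (5.0 to 31.1) | 4/7 = 57.1% (18.4 to 90.1) | 1/27 = 3.7% (0.1 to 19.0) |

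The plan as written would report the first column and could not tell A from B. The 2x2 table shows that most changes fell in concordant wrists in A (3 of 5) and in discordant wrists in B (4 of 5). The intervals overlap heavily, so the gain is in showing where the changes fell, not in a precise contrast.

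**The case against.** The best defence is that nothing essential is missing. Both diagnoses and both treatments are recorded for each patient, the objective in 3.2 is itself about intended intervention, and the deferred SAP is a normal place for such a table. This stands as far as it goes: the gap is in the analysis, not mainly in the data, and the overall rate is a legitimate endpoint. It does not remove the point, because the analysis that is written down stops at the percentage.

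A second objection is that the sizes above rest on assumed rates. That is correct. They show that the crude rate can be ambiguous, not that it will be.

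A reader might infer more than the documents support:
- *That the two treatments differ in kind, one planned and one performed.* The schematic marks only the NanoScope entry as intended, which invites this. But 7.1.1 words both in parallel, as determinations by the same attending from the findings, and the schematic puts the second inside the conventional assessment. A clarifying phrase is enough.
- *That the plan attributes every difference to diagnosis.* Section 7.1.1 frames the comparison as a question and assigns no cause to individual changes.
- *That section 7.5 distorts the rate.* It says "Treatment with additional upper extremity surgical procedures will not be permitted unless discussed with and approved by the principal investigator". This concerns additional procedures, allows them with approval, and does not differ by scope. Nothing in the documents says that treatment at the index arthroscopy counts as additional, or that approval could be refused between the two looks.

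**Conclusion.** The concern holds in a limited form. The objective asks whether diagnostic variability results in a change of intervention; the planned analysis reports only how often the intervention changed and by itself cannot answer that. This is an analysis gap in a descriptive secondary endpoint. It is not evidence that the rate is biased, and the overall rate remains informative.

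The documents give no discordance or change rates, so the size can only be illustrated. Under the stated assumptions (half of discordances change the plan, 5% to 20% discordance, 3% to 10% background change), between 21% and 80% of the crude rate would be unrelated to diagnosis; with no background change the share is zero.

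Relating change to disagreement still would not show that the instrument caused it. One unblinded operator performs both looks in a fixed order (6.3.2, 2.4.1, 10.5.2), so an instrument effect cannot be separated from the effect of looking a second time.

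**What to change.** Keep the overall change rate as the endpoint. In 10.3.3 add a per-wrist 2x2 table of treatment change (yes/no) by diagnostic disagreement between the two looks (yes/no), with a one-line rule for each yes. Report the change rate overall, among discordant wrists and among concordant wrists, each with an exact 95% confidence interval.

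Do not restrict the endpoint to changes with a disagreement on the structure treated. That would drop scope-driven changes where the recorded diagnosis agreed but visualization or confidence differed, both of which the study rates.

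In 7.1.1 and the schematic, state that the final treatment is the treatment determined from the conventional look, recorded before treatment starts. Section 7.1.1 already implies the determination; the timing of the record should be explicit.

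The cost is one extra table from data already collected and a short wording change. The drawback is imprecision. If only 3 wrists are discordant and none changes, the exact upper limit is 1 − 0.025^(1/3) = 70.8%; with 7 it is 1 − 0.025^(1/7) = 41.0%. The report should present the table as descriptive and state the second-look limitation beside it.
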